#### **8.4.9 Clinical Safety Laboratory Assessments**

See [Section 10.2](#) for the list of clinical laboratory tests to be performed and to the SoA ([Section 1.3](#)) for the timing and frequency.

In the event of an unexplained clinically-significant abnormal laboratory test value, the test should be repeated and followed up until it has returned to the normal range and/or an adequate explanation of the abnormality is found. Any clinically-significant laboratory abnormality considered an AE should be recorded in the eCRF.

Laboratory test results will be graded according to the CTCAE v. 5.0 criteria. Out of range results considered to be CS should be verified by repeat testing as soon as possible. In general, a confirmed Grade 3 or Grade 4 abnormal laboratory test result will be a CS AE and needs to be reported as such in the eCRF, unless associated with disease progression. Confirmed Grade 2 abnormal laboratory results will be assessed on a case by case basis for clinical significance based upon the subject's baseline value, the duration of the abnormal result, the need for and type of treatment and/or further evaluation required. Abnormal laboratory test results meeting SAE criteria will be reported as such.

#### **8.4.10 Safety Follow-up Phone Calls**

A safety follow-up phone call should be performed to evaluate ongoing AEs, occurrence of new AEs and use of concomitant medication the third week of each cycle, unless the subject is receiving weekly dosing.

### **8.5 Adverse Events and Serious Adverse Events**

The definitions of an AE and SAE can be found in [Section 10.3](#). For AEs of CLS, CRS/ SIRS, and IRRs, individual symptoms and grade should be reported on the appropriate eCRF.

#### **8.5.1 Time Period and Frequency for Collecting Adverse Event Information**

The AE reporting period will begin on the day of the first dose of study drug unless deemed related to a protocol screening procedure after signing informed consent until the STFU visit or phone call, or until the start of new cancer therapy (unless the investigator believes the AE is related to MT-3724), whichever occurs first.

Grade  $\geq$  2 AEs related to MT-3724 that are ongoing at the STFU Visit should be followed by the investigator until all events have resolved to Grade  $\leq$  1.

Those AEs that occur after the first dose on C1D1 will be considered treatment-emergent.

All AEs that occur in enrolled subjects during the AE reporting period specified in the protocol must be recorded, regardless of the relationship of the AE to MT-3724. Any serious known untoward event that occurs beyond the AE reporting period that the investigator assesses as at least possibly related to MT-3724 should also be reported to the sponsor.

### **8.5.2 Method of Detecting Adverse Events and Serious Adverse Events**

The method of recording, evaluating, and assessing causality of AEs and SAEs and the procedures for completing and transmitting SAE reports are provided in [Section 10.3](#).

Care will be taken not to introduce bias when detecting AEs and/or SAEs. Open-ended and non-leading verbal questioning of the subject is the preferred method to inquire about AE occurrences.

### **8.5.3 Regulatory Reporting Requirements for Serious Adverse Events**

If an SAE occurs at any time from the time of start of treatment until the STFU Visit, it must be reported to the CRO responsible for clinical safety management and the medical monitor acting on behalf of the sponsor (see list of contacts). The investigator must report any SAE due to any cause, whether or not related to the study drug(s), within 24 hours of the time when s/he became aware of the event. The investigator must send a preliminary report of any such SAE to the study safety monitor via the electronic data capture (EDC) system within 24 hours or if this is not possible, via email or fax using an SAE Report Form, or at a minimum by telephone.

The event must be recorded on the electronic SAE eCRF page. Preliminary reports of SAEs must be followed by detailed descriptions later, including clear copies of hospital case reports, consultant reports, autopsy reports, and other documents when requested and applicable. All copies should be redacted to remove subjects' personal details and annotated with the subject's unique study identifiers.

Appropriate remedial measures should be taken to treat the SAE, and the response to treatment should be recorded. Subjects must be closely followed until sufficient information is obtained to indicate a return to normal status or until the event stabilizes at a level acceptable to the investigator. Clinical, laboratory, and diagnostic measures should be employed as needed to determine the etiology of the problem. The results will be reported promptly to the sponsor.

Comprehensive SAE reporting instructions will be provided in the study manual.

### 8.5.3.1 SUSAR

An unexpected SAE that is at least possibly related to the study drug will be considered a Suspected Unexpected Serious Adverse Reaction (SUSAR).

The sponsor will determine if a reported SAE meets the criteria for SUSAR and confirm the decision with the medical monitor and the CRO responsible for clinical safety management. The sponsor has a legal responsibility to notify regulatory authorities, investigators, and in some locations Ethics Committees (ECs)/Institutional Review Boards (IRBs) regarding potentially serious risks from clinical trials. The sponsor will comply with country-specific regulatory requirements relating to safety reporting to the regulatory authority, IRBs/ ECs, and investigators.

### 8.5.3.2 Pregnancy Reporting Instructions

Pregnancy should be avoided from 4 weeks before the start of treatment, until the STFU Visit. Acceptable contraception is specified in the inclusion criteria, see [Section 5.1](#) and [Section 10.4](#).

Subjects must be advised to immediately notify the investigator of pregnancy.

If pregnancy occurs during treatment in a subject the investigator must immediately discontinue MT-3724 and report the pregnancy to the CRO responsible for clinical safety management and the medical monitor acting on behalf of the sponsor, along the same timelines as a SAE (see [Section 8.5.3](#)). The subject must be referred to an obstetrician/gynecologist experienced in reproductive toxicity for further evaluation and counseling.

For a study subject, the outcome of the pregnancy should be followed up carefully, and any abnormal outcome of the mother or the child should be reported. For the pregnancy of a study subject's partner, all efforts should be made to obtain similar information on course and outcome, subject to the partner's consent.

## 8.6 Pharmacokinetics

Blood samples will be collected prior to, during, and at specified times following the MT-3724 infusion for determination of free MT-3724 concentrations in serum, which will be used for the assessment of the single-dose and repeat-dose PK of MT-3724 (refer to [Table 1-2](#) for specific time points). If warranted, select serum samples collected for the MT-3724 concentration may also be analyzed for any other anti-CD20 biologic agent that the subject may have received prior to enrollment. Please note, samples for PK must be drawn from a different line than that used for MT-3724 administration.

In addition, for subjects who will have cerebrospinal fluid (CSF) collected at any time point in the study as part of their SoC, a portion of the sample collected will be used by the sponsor to evaluate for the presence of MT-3724 in CSF.

## 8.7 Pharmacodynamics

### 8.7.1 Peripheral Blood

Pharmacodynamic markers will be the B-cell count and the immunophenotype in peripheral blood, as determined by flow cytometry, and circulating immunoglobulins (IgA, IgG, IgM).

Serial blood samples for pharmacodynamic assessment will be collected as indicated in the SoA ([Section 1.3](#)). Unscheduled assessments may be performed at any time at the investigator's discretion.

### 8.7.2 Optional Tumor Tissue Biopsy

Optional biopsy of the tumor tissue may be performed at the EoT Visit in those subjects who had been discontinued due to PD, had consented for this procedure and have accessible peripheral lymph node(s).

The purpose of the biopsy is to assess if the disease progression is associated with the loss of CD20 positivity of tumor cells.

Subjects may also have a biopsy to confirm CR, in the absence of PET/CT scans.

## 8.8 Immunogenicity Assessments

Antibodies to MT-3724 will be evaluated in blood samples collected from all subjects according to the SoA ([Section 1.3](#)). Additionally, blood samples should also be collected at the final visit from subjects who discontinued study intervention or were withdrawn from the study. These samples will be tested by the sponsor or sponsor's designee.

Blood samples will be screened for anti-drug antibodies (ADA) that bind MT-3724. All ADA positive samples will have the titer reported and screened for neutralizing antibodies (NAb), reported as positive or negative. Other analyses may be performed such as verifying the stability of antibodies to MT-3724.

The detection and characterization of antibodies to MT-3724 will be performed using a validated assay method by or under the supervision of the sponsor. All samples collected for detection of antibodies to MT-3724 will also be evaluated for MT-3724 serum concentration to enable interpretation of the antibody data. Antibodies may be further characterized and/or evaluated for their ability to neutralize the activity of the study intervention(s). Refer to the appropriate informed consent for the maximum duration of storage. Samples will be stored at a facility selected by the sponsor to enable further analysis of immune responses to MT-3724.

## 9 STATISTICAL CONSIDERATIONS

The statistical analysis of the clinical data will be performed by Molecular Templates' representative. Analysis of the PK, pharmacodynamic and immunogenicity data may be performed separately and entered into a separate database. Data from the clinical, PK and pharmacodynamic databases will be integrated in the clinical study report.

Summary statistics for continuous variables will include the mean, standard deviation, median, and range (minimum/maximum); categorical variables will be presented as frequency counts and percentages; and time-to-event variables will be summarized by Kaplan-Meier plots, medians and range. Where confidence limits are appropriate, the confidence level will be 95% (2-sided), unless otherwise stated. There are no inferential statistical methods for this study design.

Individual data (including relevant derived variables) will be presented by variable in by-subject listings. Results of statistical analyses, descriptive summary statistics and supportive listings will also be presented.

Detailed methodology for summary and statistical analyses of the data collected in Parts 3 and 4 of this study will be documented in a statistical analysis plan, which will be maintained by the sponsor. This document may modify the plans outlined in the protocol; however, any major modifications will also be reflected in a protocol amendment and documented in the clinical study report.

Statistical analyses will be performed using SAS® v9.4 or higher (SAS Institute, Cary NC, USA).

### 9.1 Statistical Hypothesis and Sample Size Determination

In Part 3, approximately 25 subjects will be enrolled as a continuation of the expansion of the MTD cohort with the intention to verify the safety, dose and dosing schedule (completion of the Phase 1b).

In Part 4, approximately 88 evaluable subjects will be enrolled. If at least 23 of 88 evaluable subjects respond at the end of Part 4, then the null hypothesis is rejected in favor of the alternative hypothesis and the effectiveness of MT-3724 as monotherapy will have been proven. Under the stated null and alternative hypotheses, Part 4 carries 90.4% power at the 1-sided alpha level of < 0.025.

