**Number of Subjects:**

Approximately 113 subjects with histologically confirmed, relapsed or refractory DLBCL: approximately 25 in Part 3 and approximately 88 evaluable subjects in Part 4. Additional subjects may be enrolled to ensure an adequate number of evaluable subjects in Part 4.

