#### **4.1.2      Part 4**

The goal of Part 4 is to provide sufficient evidence to test the null hypothesis that the true response rate with MT-3724  $\leq$  17% vs the alternative hypothesis that the true response rate with MT-3724  $\geq$  32% at the 1-sided alpha level of 0.025 with high statistical power. At least 88 evaluable subjects will be required to test the null hypothesis vs the alternative hypothesis in Part 4. If at least 23 of 88 subjects respond at the end of Part 4, then the null hypothesis is rejected in favor of the alternative hypothesis and the effectiveness of MT-3724 as monotherapy will have been proven. Under the stated null and alternative hypotheses, Part 4 carries 90.4% power at the 1-sided alpha level of < 0.025.

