## 9.2 Populations for Analyses

For purposes of analysis, the following populations are defined:

Population	Description
Full analysis set (FAS) population	All subjects who received at least 1 dose of MT-3724 monotherapy treatment. This will be the primary population for the assessment of efficacy endpoints.
Modified full analysis set (mFAS) population	All subjects who have at least 1 post-baseline efficacy assessment; subjects without a post-baseline efficacy assessment will not be considered evaluable for the primary efficacy analysis. Subjects who discontinue due to disease progression or die, prior to disease assessment will be included.
PK analysis population	All subjects who received any amount of MT-3724 and for whom the on-treatment PK data are considered to be sufficient and interpretable.
Immunogenicity analysis population	All subjects who have received any amount of MT-3724 and have valid post-baseline immunogenicity assessment will be included in the analysis set for the immunogenicity analysis.
Pharmacodynamic analysis population	All subjects who have received any amount of MT-3724 and have at least 1 valid post-baseline pharmacodynamic assessment.
Safety analysis population	All subjects who received at least 1 dose of MT-3724 monotherapy treatment. For this study, this is equivalent to the FAS population.

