### **9.3.2.1        Primary Efficacy Variable (for Part 4)**

The primary efficacy variable is the ORR. The ORR is defined as the percent of subjects with CR or PR determined by the blinded, ICR according to the Lugano Classification for Lymphoma ([Cheson, 2014](#)), relative to the FAS population.

Overall response rate will be summarized by number and percentage of subjects meeting the definition of ORR along with the corresponding 2-sided 95% binomial exact confidence intervals (CI), separately for Parts 3 and 4.

In Part 4, with  $n = 88$  subjects, if  $\geq 23$  ORRs are seen, the null hypothesis is rejected in favor of the alternative hypothesis and the effectiveness of MT-3724 as monotherapy will have been proven.

Subjects with missing disease assessments such that objective response cannot be determined will be assumed to be non-responders in the analysis.

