2. SUBJECT POPULATION

2.1. Population Definitions

The following subject populations will be evaluated and used for presentation and analysis of the data:

- Safety Set (SS): All subjects who received any amount of MT-3724.
- Pharmacokinetic Analysis Set (PAS): All subjects from the Safety Set with sufficient serum concentration data to determine the primary PK parameters.
- Full Analysis Set (FAS): All subjects from the Safety Set who have at least one tumor re-evaluation performed (scheduled or unscheduled).

The Safety Set is the primary population for the analysis of safety. The PAS is the primary population for all PK and PDn analyses. The FAS is the primary population for all exploratory efficacy analyses.

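### The Part 4 test has conflicting denominators: the cut-off is set on 88 evaluable subjects, the primary response rate is on all treated subjects, and no cut-off is given for any other N

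*Protocol*

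**What the plan says.** **Evaluable subjects as denominator.** Protocol section 9.1: "If at least 23 of 88 evaluable subjects respond at the end of Part 4, then the null hypothesis is rejected". Section 4.1.2 and the synopsis design text make 88 evaluable subjects a minimum, not a cap. The modified FAS (mFAS) row of section 9.2 states who is not evaluable: "subjects without a post-baseline efficacy assessment will not be considered evaluable for the primary efficacy analysis". The same row keeps in the mFAS those who stop for progression, or die, before any assessment.

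**All treated subjects as denominator.** The FAS row of section 9.2 covers everyone given at least one dose and adds: "This will be the primary population for the assessment of efficacy endpoints". Section 9.3.2.1 calculates the primary response rate relative to the FAS, plans an exact 2-sided 95% interval, and says: "Subjects with missing disease assessments such that objective response cannot be determined will be assumed to be non-responders in the analysis". It repeats the threshold of 23 for n = 88 subjects, without the word evaluable.

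**Size of the FAS.** The synopsis says: "Additional subjects may be enrolled to ensure an adequate number of evaluable subjects in Part 4". Section 7.2 provides replacement for subjects never dosed and for those not evaluable for dose decisions in the DLT period. A dosed Part 4 subject who is never assessed therefore stays in the FAS.

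**Whether there is a test at all.** The opening of section 9 says: "There are no inferential statistical methods for this study design". Sections 4.1.2, 9.1 and 9.3.2.1 describe a formal test.

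**The concern.** The same subject, treated but never assessed, is excluded from the primary analysis by one row of the section 9.2 table. The next row up and section 9.3.2.1 count that subject as a failure. The only threshold fits one sample size, which the protocol does not fix. The protocol also does not say whether the 17% null rate refers to evaluable or to all treated subjects.

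Two analysts could both follow the text and reach different decisions. With 88 evaluable subjects, a FAS of 92 and 23 responders, one declares effectiveness proven under section 9.1. The other reports a FAS interval that still contains the null rate. Part 4 is single-arm and open-label, so a denominator chosen after responses are known would be open to the charge of being chosen for its result.

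**Working it through.** **Inputs.** Null rate 17%, alternative 32% and 1-sided alpha 0.025 (section 4.1.2); threshold 23 of 88 and power 90.4% (section 9.1). The documents give no unevaluable rate, so the FAS sizes below are illustrations.

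**Step 1: reproduce the plan.** With X ~ Binomial(N, p):
- alpha = P(X ≥ 23 | 88, 0.17) = 0.0201
- power = P(X ≥ 23 | 88, 0.32) = 0.9039
- a threshold of 22 would give alpha 0.0364, so 23 is the smallest valid threshold.

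The protocol's figures are right at N=88.

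**Step 2: keep 23, let the FAS grow, and apply the rates to all treated subjects.** The lower limit is the exact (Clopper-Pearson) 2-sided 95% limit for 23 responders.

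| FAS N | P(X ≥ 23) at 17% | P(X ≥ 23) at 32% | Lower limit, 23/N |
|---|---|---|---|
| 88 | 0.0201 | 0.904 | 17.3% |
| 89 | 0.0229 | 0.915 | 17.1% |
| 90 | 0.0259 | 0.925 | 16.9% |
| 95 | 0.0460 | 0.962 | 16.0% |
| 100 | 0.0754 | 0.982 | 15.2% |

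Alpha passes 0.025 at N=90. From there the interval for 23 responders includes 17%.

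**Step 3: keep 23, with exactly 88 evaluable and every extra FAS subject a non-responder.** Responders can come only from the 88, so alpha stays 0.0201 and power 0.904 at any FAS size. If evaluability is instead treated as random, so that the FAS rate is 0.17 × 88/N, alpha is 0.0204 at N=90, 0.0210 at N=95 and 0.0215 at N=100. All are below 0.025. The FAS interval for 23 responders still includes 17% from N=90, so the rule and the interval disagree even though the error rate holds.

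**Step 4: cut-off by actual FAS size.** The smallest r with P(X ≥ r | N, 0.17) ≤ 0.025 is the same r at which the exact lower limit first exceeds 17%:

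| FAS N | Critical count |
|---|---|
| 85–89 | 23 |
| 90–94 | 24 |
| 95–99 | 25 |
| 100–104 | 26 |

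**Step 5: power with the Step 4 cut-offs.**
- *32% applies to all treated:* 88.6% at N=90 (cut-off 24), 92.0% at N=93 (24), 93.4% at N=98 (25).
- *88 evaluable at 32%, the rest non-responders:* P(X ≥ 24 | 88, 0.32) = 85.7% for FAS 90–94, and P(X ≥ 25 | 88, 0.32) = 79.7% for FAS 95–99. Using the diluted rate 0.32 × 88/N gives 85.4% at N=93 and 79.1% at N=98.

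**Step 6: how often the readings part.** With 88 evaluable and a FAS of 90–94, they differ only at exactly 23 responders. That probability is 0.0201 − 0.0106 = 0.0095 at 17%, and 0.9039 − 0.8571 = 0.047 at 32%. For FAS 95–99 they differ at 23 or 24 responders: 0.0201 − 0.0053 = 0.0148 and 0.9039 − 0.7973 = 0.107.

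**The case against.** The strongest reply is that the protocol never applies 23 to another N. Section 9.3.2.1 ties the rule to 88 subjects. If the FAS grows only because unevaluable subjects are made up for, the additions cannot respond and 23 keeps its error rates (Step 3). The band of disagreement is narrow (Step 6), and the planned FAS interval would show whether 17% is excluded. All of this stands. It makes the defect an undefined cut-off with conflicting denominators, not a stated rule with wrong error rates.

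Four stronger readings are tempting and are not supported:

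- *The FAS will exceed 88.* The synopsis says only that additional subjects may be enrolled.
- *The evaluable set removes early failures.* The mFAS keeps those who progress or die before assessment. Only subjects who leave unassessed for other reasons, such as toxicity or withdrawn consent, drop out.
- *The 90.4% power requires that no treated subject be unevaluable.* With 88 evaluable and 23 kept, power is 90.4% whatever the FAS size. If 32% applies to all treated subjects, a fixed 23 gives more power as N grows. Power is lost when the cut-off is raised to suit a FAS enlarged by non-responders.
- *The SAP's narrower FAS, limited to re-scanned subjects, governs Part 4.* That SAP is based on protocol v7.0, covers Parts 1 and 2 with the extension study, and plans no hypothesis test. It neither causes nor resolves this conflict.

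**Conclusion.** The conflict is in the current protocol text and affects the Part 4 primary decision. The stated alpha and power are correct at N=88, and alpha still holds at N=89.

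Beyond that, the result depends on what the null rate refers to. If 17% is the rate among all treated subjects and 23 is kept, alpha exceeds 0.025 from N=90. If 88 are evaluable and the rest are non-responders, alpha holds, but from N=90 exactly 23 responders meets the rule while the FAS interval includes 17%. Inflation is therefore conditional, while the missing rule for N other than 88 is not. The FAS sizes above 88 are assumptions. The conclusion that one population and one cut-off rule must be named does not depend on them.

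**What to change.** 1. In sections 4.1.2, 9.1 and 9.3.2.1 and the synopsis, name the FAS as the single population for the test, with missing counted as non-response. This follows what section 9.2 (FAS row) and section 9.3.2.1 already call primary.
2. Replace the fixed count with a rule valid at any size: reject the null hypothesis if the lower limit of the exact 2-sided 95% interval, at the actual FAS N, is above 17%. Print the Step 4 critical counts beside it.
3. Delete the mFAS clause that makes unassessed subjects not evaluable for the primary analysis. Keep the mFAS as a sensitivity analysis.
4. Correct the section 9 sentence that denies inferential methods, so that it excepts the Part 4 primary test.
5. Restate power under an unevaluable fraction labelled as an assumption. With 88 evaluable at 32% and the rest non-responders, power is about 85–86% at FAS 90–94 and about 79–80% at FAS 95–99. If 90% is wanted under that assumption, the sample size has to be reconsidered.

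Items 1 to 4 cost protocol wording only, to be carried into the SAP for Parts 3 and 4. Item 5 makes the stated power less favourable. The change should be made before Part 4 response data are seen.
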